**Table 1-1: Schedule of Activities**

Period	Scr a	Treatment Period (24 Weeks)												EOT/EDisc	SFU	EOS	Unsch								
Visit type	S	S	TH b	S	S	S	TH c	1 d	S	S	S														
Procedure																									
Informed consent	X																								
Verification of inclusion/exclusion criteria	X	X e																							

**Table 1-1: Schedule of Activities**

Period	Scr a	Treatment Period (24 Weeks)																		EOT/EDisc	SPU	EOS	Unsch				
		S	S	S	TH b	S	S	S	S	TH c																	
Visit type	S	S	S	TH b	S	S	S	S	TH c	S	TH c	S	TH c	S	TH c	S	TH c	S	T d	S	S						
Procedure																											
Demography	X																										
Randomization		X																									
Full neurological examination & full PE f	X																								X		X
Brief neurological examination & brief PE f		X						X		X		X		X		X										X	
LGI1 detection	X																										
Study withdrawal criteria		X	X	X	X	X	X	X	X	X	X	X	X	X	X	X	X	X	X	X	X	X	X	X	X		

**Table 1-1: Schedule of Activities**

Period	Treatment Period (24 Weeks)																		EOT/EDisc	SFU	EOS	Unsch	
	Scr a	S	S	TH b	S	S	S	S	TH c	TH c	TH c	TH c											
Visit type	S	S	TH b	S	S	S	S	TH c	S	TH c	S	TH c	S	TH c	S	TH c	S	TH c					
Procedure																							
C-SSRS g	X	X	X		X	X	X	X	X	X	X	X	X	X	X	X	X	X	X	X	X	X	X
General medical/ procedure history	X																						
Contact IRT		X		X	X	X	X	X	X	X	X	X	X	X	X	X	X	X	X	X			
Pregnancy test (serum)	X																						
Pregnancy test (urine) h		X		X		X		X		X		X		X		X					X	X	O
FSH test i	X																						
Hematology, chemistry o , urinalysis	X	X		X		X		X		X		X		X		X		X		X	X	X	X

**Table 1-1: Schedule of Activities**

Period	Treatment Period (24 Weeks)																		EOT/EDisc	SFU	EOS	Unsch		
	Scr a																							
Visit type	S	S	TH b	S	S	S	S	TH c																
Procedure																								
Serology testing (HIV, Hepatitis B and Hepatitis C)	X																							
IGRA TB test j	X																							
12-lead ECG	X																							X
Vital signs k	X	X		X	X	X	X	X	X	X	X	X	X	X	X	X	X	X	X	X	X	X	X	X
Record AE	X	X	X	X	X	X	X	X	X	X	X	X	X	X	X	X	X	X	X	X	X	X	X	X
Record prior and concomitant (including rescue) medications	X	X	X	X	X	X	X	X	X	X	X	X	X	X	X	X	X	X	X	X	X	X	X	X

**Table 1-1: Schedule of Activities**

Period	Treatment Period (24 Weeks)																		EOT/EDisc	SFU	EOS	Unsch			
	Scr a																								
Visit type	S	S	S	TH b	S	S	S	S	TH c	S	T d	S	S												
Procedure																									
Blood sampling for PK of RLZ m		X	X				X		X		X		X		X				X	X	X	X		O	
Blood sampling for DNA and RNA analysis		X																							
Serum complement [REDACTED] and plasma complement [REDACTED] n		X																							
Total IgG o,p	X	X		X	X	X	X	-/X/-	X	-/X/-	X	-/X/-	X	-/X/-	X	-/X/-	X				X		X	O	

**Table 1-1: Schedule of Activities**

Period	Treatment Period (24 Weeks)																EOT/EDisc	SFU	EOS	Unsch				
	Scr a																							
Visit type	S	S	TH b	S	S	S	S	TH c	S	T d	S	S												
Procedure																								
IgG subclasses		X																					X	
██████████		X																					X	
LGI1 IgG (total and subclasses) serum quantification		X		X		X		X		X		X		X								X	X	
Anti-drug antibodies q	X	X				X		X		X		X		X								X	X	X
CSF sample collection for LGI1 r	O																					O		

**Table 1-1: Schedule of Activities**

Period	Treatment Period (24 Weeks)																		EOT/EDisc	SPU	EOS	Unsch			
	Scr a																								
Visit type	S	S	TH b	S	S	S	S	TH c	T d	S															
Procedure																									
Blood sampling for exploratory biomarker analysis s		X																						X	
Seizure evaluation t	X	X		X	X	X	X	X	X	X	X	X	X	X	X	X	X	X	X	X	X	X	X	X	
Provide seizure diary	X																								
Medical resource utilization	X	X	X	X	X	X	X	X	X	X	X	X	X	X	X	X	X	X	X	X	X	X	X	X	
RBANS v	X							X				X				X						X		O	
mRS w	X	X						X				X				X						X		O	
CGI-S y	X						X				X				X						X			O	

**Table 1-1: Schedule of Activities**

Period	Treatment Period (24 Weeks)																		EOT/EDisc	SFU	EOS	Unsch				
	Scr a																									
Visit type	S	S	TH b	S	S	S	S	TH c	S	T d	S	S														
Procedure																										
SF-36		X									X												X		O	
EQ-5D-5L		X									X												X		O	
MRI scan u	X																						X			

ADA=antidrug antibody; AE=adverse event; BL=Baseline (predose); BP=blood pressure; XXXXXXXXXX

CGI-S=Global Impression of Disease Severity; CSF=cerebrospinal fluid; C-SSRS=Columbia Suicide Severity Rating Scale; CT=computed tomography;

Disc.=discontinuation; DNA=deoxyribonucleic acid; ECG=electrocardiogram; EDisc=Early Discontinuation Visit; EOS=end of study; EOT=end of treatment; EQ-5D-5L=EuroQol-5D-5L; FSH=follicle stimulating hormone; GI=gastrointestinal; HIV=human immunodeficiency virus; Ig=immunoglobulin; IGRA=interferon-gamma release assay; IMP=investigational medicinal product; IRT=interactive response technology; IVMP=intravenous methylprednisolone; LGI=leucine-rich glioma inactivated 1; MRI=magnetic resonance imaging; mRS=Modified Rankin Scale; No.=number; O=optional; PD=pharmacodynamic; PE=physical examination; Per.=Period; PK=pharmacokinetic(s); Proc.=Procedure; RBANS=Repeatable Battery for the Assessment of Neuropsychological Status; RLZ=rozanolixizumab; RNA=ribonucleic acid; S=site visit; Scr=Screening; SFU=Safety Follow-up; SF-36=36-item Short Form Survey; T=telephone call; TB=tuberculosis; TH=telephone call and home visit; Unsch=Unscheduled Visit

a Recording of seizures will be initiated and conducted on each day of Screening. These daily seizure recordings will be used to calculate the Baseline seizure frequency.

b The study participant will be telephoned by a qualified site personnel and be assessed for AEs, concomitant medications, withdrawal criteria, and the seizure diary. A healthcare professional will also visit the study participant at their home to collect PK samples. Alternately, the visit can be conducted at the site as deemed necessary by site personnel and/or the study participant. There should be at least 1 day between visits.

c Visits may be performed by a healthcare professional visiting the study participant at their home. During the home visit, a qualified site personnel will assess AEs, concomitant medications, withdrawal criteria, and the seizure diary by telephone call prior to IMP administration. Alternately, the visits can be conducted at the site as deemed necessary by site personnel and/or the study participant. Feasibility of IMP dosing in a home setting must be confirmed before the visit is conducted.

d During the SFU phone call, the qualified site personnel will assess AEs, concomitant medications, and evaluation of seizure diary by telephone.

u For eligibility criteria, the laboratory and body weight data from Screening will be used. However, the urine pregnancy test at Visit 2 also must be negative for eligibility.

f A brief PE can also be performed on the occurrence of an AE. A full or brief PE should include evaluation for medical history and for signs and symptoms of latent or active TB and for risk factors for exposure to TB at the following time points: Screening, Baseline, W13, W21, EDisc if applicable and EOS (see Section 10.12). A full neurological examination should also be performed for any study participant who experiences severe and/or serious headache and for study participants with suspected aseptic meningitis. For details of the assessments included in these examinations see Section 8.2.1 (description of full and brief PE), and Section 8.2.2 (description of full and brief neurological examination).

g A full C-SSRS assessment will be performed only when the study participant has a positive response to the suicidal ideation query. If a study participant has active suicidal ideation as confirmed by the answer 'Yes' to Question 4 or Question 5 of the C-SSRS assessments, the study participant will be excluded or withdrawn from the study and immediately referred to a mental healthcare professional.

h A urine pregnancy test will be performed using a dipstick test; a positive urine pregnancy test must be confirmed using a serum pregnancy test. The serum pregnancy test must be negative before dosing.

i The FSH test will only be performed to confirm menopausal status in female study participants (as applicable).

j The IGRA test will be performed by a local laboratory. Study participant should not be dosed in case of any positive IGRA or 2 indeterminate IGRA until the study participant has been evaluated by a TB specialist. Further details are provided in Section 10.12.

k Vital signs comprise systolic and diastolic BP, pulse rate, and temperature.

l The interval between administration of 2 consecutive rozanolixizumab doses should be  $7 \pm 2$  days. On dosing days for the first 2 weeks (Visit 2 and Visit 5), a 4-hour post-dose observation will be in place. Assuming the first 2 doses were well tolerated, on dosing days in Week 3, 4, and 5 (Visit 6, Visit 7, and Visit 8), a 1-hour post dose observation will be in place. Assuming the first 5 doses were well tolerated, on subsequent weeks, a 15-minute post-dose observation will be in place. Following a missed dose due to temporary IMP discontinuation, a 1-hour observation will be in place for the first 2 doses followed by a 15 minute observation per above. The minimum post dose observation time frame may be extended at the discretion of the investigator or study nurse at home dosing visits. These recommendation are applicable for dosing at site and at home except where specified.

m At Visits 2, 8, 12, 16, 22, and 29, blood samples for PK will be obtained predose. At nondosing Visits 3, 30, 31, and 32, samples will be obtained once during the visit.

n Serum and plasma complements are to be obtained predose at Baseline (Day 1) for all study participants.

o Ad hoc assessments of IgG and albumin can be performed to monitor the recovery of IgG and albumin levels, or for random sampling of study participants to maintain the blind. These results will be reviewed by the unblinded medical monitor only (Section 7.1.4).

p For Visits 9–11, Visits 13–15, Visits 19–21, and Visits 23–25, samples for total IgG assessments are only required to be taken at the middle visit (ie, Visits 10, 14, 20, and 24). In the table, the samples required at these visits are described as '-/X/-' representing no sample (-)/sample (X)/no sample (-).

q For study participants who withdraw from the study, a sample should be taken for ADA analysis upon his/her EDisc Visit. A Screening sample will be taken for the purpose of assay parameter characterization (eg, setting ADA cut points and PK selectivity assessments).

r This optional CSF sample will be used to test for LGI1 autoantibodies using an independent research-use only, quantitative assay (flow cytometry LGI1 assay). Further details are provided in Section 8.9.

s Exploratory biomarker samples will be taken predose at Baseline (Day 1) and at EOT/EDisc Visit for all study participants. In study participants who experience severe and/or serious headaches or suspected aseptic meningitis, samples should also be taken 4 hours after the onset of the event, or otherwise as soon as possible within 72 hours after the onset of the event.

t Seizure data should be recorded in the seizure diary starting from the day of consent.

u MRI should be collected per local guidelines during the Screening Period or at the Baseline Visit. A MRI performed within 3 months of the Screening Period may also be acceptable as per the investigators judgement. Additional MRI may be performed at any timepoint in the study as deemed necessary by the investigator/local radiologist.

v The assessments of RBANS and CGI-S should be performed as close as possible prior to the Baseline Visit.

w The assessment of mRS at Screening should be performed as close as possible to consent.

x Visit 17 and Visit 18 were removed in Protocol Amendment 4; however, the Visit schedule was not renumbered.

y Visit 4 was removed in Protocol Amendment 5; however, the Visit schedule was not renumbered.

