### **Treatment Groups and Duration**

The maximum study duration per study participant is upto 38 weeks. There are 3 study periods:

- Screening Period: Eligibility will be assessed during the Screening Period of up to 42 days. If a study participant becomes seizure free as a result of steroid treatment, the participant may still be randomized in the study, providing the prior occurrence of seizures is well documented.

Following screening and completion of the Baseline assessments, treatment will be initiated in study participants who are deemed appropriate for initiation or re-initiation of high dose corticosteroids (500 to 1000mg methylprednisolone [MP] equivalent /day) based on clinical symptoms and history, or who have initiated corticosteroids within 42 days prior to randomization at a dose of 500 to 1000mg MP equivalent/day. Corticosteroids can be initiated prior to the start of the Screening Period, however, the study participant must be randomized within 42 days of corticosteroids initiation. If the study participant has initiated a steroid taper, the study participant cannot receive oral steroids at a dose lower than 40mg/day when randomized. Study participants receiving a steroid dose of 60mg/day, 50mg/day or 40mg/day at the time of randomization, will have to maintain that dose for 7 days ( $\pm 2$  days), 14 days ( $\pm 2$  days) or 21 days( $\pm 2$  days), respectively, before resuming [REDACTED] down-titration steps. Each subsequent down-titration step will last for 7 days ( $\pm 2$  days; see Section 1.2). For those participants that have not initiated a steroid taper, the down-titration of the oral steroid dose will begin after at least 3 days on the initial high dose corticosteroids, as per investigator' discretion.

- Treatment Period: Participants who have been confirmed eligible will be randomized in a 1:1 ratio to receive rozanolixizumab [REDACTED] or placebo at [REDACTED] intervals over a 24-week Treatment Period. Initially, study participants will receive rozanolixizumab or placebo in addition to intravenous (iv) or oral steroids that will be tapered as described in Section 1.2.
- Safety Follow-Up Period: Study participants who complete the 24-week Treatment Period or prematurely discontinue IMP, as well as study participants who receive rescue medication during the 24-week Treatment Period will undergo the End of Treatment (EOT) Visit/EDisc

[figure not shown]

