### 1.3 Schedule of activities

The Schedule of Activities is provided in [Table 1-1](#). Visit 32 (Week 25) is designated as the EOT Visit however, study participants that undergo early discontinuation will undergo these assessments as part of the EDisc Visit, which may occur at any week of Treatment Period. Study participants who undergo the EDisc Visit should then follow the same temporal schedule for subsequent visits (ie, complete the SFU phone call and EOS Visit at 3 and 7 weeks after the EDisc Visit, respectively).

Some study-specific investigations may not be conducted according to the study protocol during a pandemic or other exceptional circumstances due to the need to implement safety measures and guidance from regulatory authorities (see [Section 8](#) for further information).

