- The participant is considered to have been under treated in the opinion of the investigator

AND

- Currently the participant is experiencing a seizure rebound that requires initiation or re-initiation of high dose corticosteroids (500-1000mg MP equivalent /day) in the opinion of the investigator.

Following screening and completion of the Baseline assessments, treatment will be initiated in study participants who are deemed appropriate for initiation or re-initiation of high dose corticosteroids (500 to 1000mg MP equivalent/day) based on clinical symptoms and history, or who have initiated corticosteroids within 42 days prior to randomization at a dose of 500 to 1000mg MP equivalent/day. Corticosteroids can be initiated prior to the start of the Screening Period, however, the study participant must be randomized within 42 days of corticosteroids initiation. If the study participant has initiated a steroid taper, the study participant cannot receive oral steroids at a dose lower than 40mg/day when randomized. Study participants receiving a steroid dose of 60mg/day, 50mg/day or 40mg/day at the time of randomization will have to maintain that dose for 7 days ( $\pm 2$  days), 14 days ( $\pm 2$  days) or 21 days( $\pm 2$  days), respectively, before resuming [REDACTED] down-titration steps. Each subsequent down-titration step will last for 7 days ( $\pm 2$  days; see Section 1.2). For those participants that have not initiated a steroid taper, the down-titration of the oral steroid dose will begin after at least 3 days on the initial steroid dose, as per investigator.

- Treatment Period: Participants who have been confirmed eligible will be randomized in a 1:1 ratio to receive rozanolixizumab [REDACTED] or placebo at [REDACTED] intervals over a 24-week Treatment Period. Initially, study participants will receive rozanolixizumab or placebo in addition to iv or oral steroids that will be tapered as described in Section 1.2.
- Safety Follow-Up Period: Study participants who complete the 24-week Treatment Period or prematurely discontinue IMP, as well as study participants who receive rescue medication during the 24-week Treatment Period will undergo the EOT Visit/EDisc Visit and enter the SFU Period. At 4 weeks after the final dose, study participants will undergo a SFU phone call, and at 8 weeks after the final dose, study participants will undergo the EOS Visit.

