### **7.1      Discontinuation of study medication**

Participants who are permanently discontinued from IMP will undergo an EDisc and SFU Visit. In addition to algorithmic stopping criteria, management of AEs is ultimately at the investigator's discretion.

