### 7.1.2 Permanent discontinuation due to other AEs

Study participants **must be permanently discontinued from IMP** if any of the following safety-related events occur:

1. Study participant develops an illness that would interfere with his/her continued participation.
2. Study participant has a significant infective episode including but not limited to bacteremia/sepsis, infectious meningitis, septic arthritis, osteomyelitis, complicated pneumonia, or visceral abscess which may or may not result in hospitalization. This list is not intended to be all inclusive, and the investigator is expected to apply their judgement on continuing IMP based on the clinical situation (see Appendix 14; Section [10.14](#)).

---

3. Study participant has an AE of severe or serious hypersensitivity infusion-related reaction (see Appendix 15; Section 10.15) or anaphylaxis requiring corticosteroid and/or epinephrine therapy (Sampson et al, 2006).
4. Study participant has a recurrence of aseptic meningitis (Section 10.13).
5. Study participant who develops active TB, LTBI, or NTM infection during the study, regardless of initiation of TB treatment.
6. Study participant has active suicidal ideation as indicated by a positive response (Yes) to either Question 4 or Question 5 of the “Since Last Visit” version of the C-SSRS. The study participant should be referred immediately to a mental healthcare professional.
7. Study participant has new onset or recurrent neoplastic disease (except for superficial basal or squamous cell carcinoma of the skin not requiring targeted biological therapy, chemotherapy or radiation).

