#### **7.1.3 Permanent discontinuation due to absence or loss of clinical benefit**

Study participants **must be permanently discontinued from IMP** if they do not experience a clinical improvement within the first 4 weeks of the Treatment Period (ie, an absence of clinical benefit) or if they experience clinical worsening (ie, a loss of clinical benefit) at any time as defined by any of the following:

1. mRS assessment
  - a. Worsening of 1 point compared with Baseline; or
  - b. Lack of improvement of a severe score (4 or 5) after 4 weeks
2. Worsening of cognitive function: A decrease of  $\geq 8$  points in the total RBANS score compared to Baseline, and per the assessment of the investigator that the study participant has worsened
3. A clinically meaningful recurrence of seizures of a previously experienced type or a new seizure type, either of those requiring a change in therapy (per the assessment of the investigator)
4. Lack of seizure improvement (per the assessment of the investigator)

If study participant permanently discontinues from IMP for any reason, investigators should contact the medical monitor, whenever possible, to discuss the withdrawal of a participant in advance. Study participants who permanently discontinue the IMP should complete the assessments outlined for the EOT/EDisc Visit and enter the 8-week SFU Period. If IMP is permanently discontinued, the requirement for, and selection of, rescue therapy will be made by the investigator.

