### **7.2.1 Study withdrawal criteria**

Study participants **must be withdrawn from the study** if any of the following events occur:

1. Participant withdraws his/her consent.
2. The sponsor or a regulatory agency requests withdrawal of the participant.
3. Study participant becomes pregnant during the study, as confirmed by a positive serum pregnancy test.

Study participants **may be withdrawn from the study** at the discretion of the investigator, if the study participant is persistently noncompliant with the study procedures or medications and this noncompliance is not manageable in the opinion of the investigator.

Study participants who choose to withdraw from the study during the Treatment Period should complete the assessments outlined for the EOT/EDisc Visit.

Study participants who are withdrawn from the study during the Treatment Period should complete the assessments outlined for the EOT/EDisc Visit and be encouraged to enter the 8-week SFU Period.

Investigators should contact the medical monitor, whenever possible, to discuss the withdrawal of a study participant in advance.

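### Table 1-1 footnote g withdraws a participant from the study for an on-study Yes to C-SSRS Question 4 or 5, where Section 7.1.2 stops IMP only and Section 7.2.1 does not list the event

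*Protocol*

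**What the plan says.** Footnote g to the Schedule of Activities (protocol Table 1-1) covers a Yes to Question 4 or 5 at any C-SSRS assessment. Its instruction is that "the study participant will be excluded or withdrawn from the study and immediately referred to a mental healthcare professional".

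Section 7.1.2 lists the events for which IMP must be permanently stopped. Item 6 reads "Study participant has active suicidal ideation as indicated by a positive response (Yes) to either Question 4 or Question 5", using the since-last-visit version of the scale, and it also calls for immediate referral to a mental healthcare professional.

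Section 7.2.1 lists three events that require withdrawal from the study: withdrawal of consent, a request by the sponsor or a regulator, and pregnancy. Suicidal ideation is not among them. The only discretionary item there is noncompliance that cannot be managed.

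Follow-up is worded differently on the two routes:

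- After permanent IMP discontinuation, Section 7.1 says "Participants who are permanently discontinued from IMP will undergo an EDisc and SFU Visit". Section 7.1.3 says "Study participants who permanently discontinue the IMP should complete the assessments outlined for the EOT/EDisc Visit and enter the 8-week SFU Period".
- After being withdrawn from the study, Section 7.2.1 says the participant "should complete the assessments outlined for the EOT/EDisc Visit and be encouraged to enter the 8-week SFU Period".

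**The concern.** A positive answer to Question 4 or 5 is a safety-critical event, and sites should find one instruction for it. The Schedule of Activities is a working reference at visits. A site that reads footnote g will withdraw the participant from the study; a site that reads Section 7.1.2 will stop IMP and keep the participant in the study.

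Two things are at stake. The first is the strength of the follow-up instruction: entry into the Safety Follow-Up (SFU) Period is stated on one route and only encouraged on the other. The second is disposition. The same event could be recorded as a study withdrawal at one site and as an IMP discontinuation at another, and these categories are reported separately.

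**Working it through.** This is mainly a comparison of text.

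**Step 1: same trigger.** Footnote g covers Screening and on-study assessments together. Exclusion applies at Screening, where exclusion criterion 13 uses the same two questions. Withdrawal from the study is therefore the footnote's on-study instruction, and its trigger is the one in Section 7.1.2 item 6.

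**Step 2: different actions.**

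| Source | On-study action | Referral | SFU wording |
|---|---|---|---|
| Table 1-1, footnote g | Withdraw from study | Immediate | Encouraged (through Section 7.2.1) |
| Section 7.1.2, item 6 | Permanently stop IMP | Immediate | Enter SFU (through Sections 7.1 and 7.1.3) |
| Section 7.2.1, mandatory list | Event not listed | Not stated | Not applicable |

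Section 8.2.7 adds a third, softer wording: for signs of suicidal ideation or behavior in general, stopping IMP is to be considered.

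**Step 3: are the two actions synonyms in this protocol?** No.

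- Sections 7.1 and 7.2 are separate, each with its own criteria.
- Section 9.3.1.1 distinguishes leaving randomized treatment and entering the SFU from complete withdrawal from the study.
- Appendix 6 (liver safety) stops study medication permanently and keeps the participant in the study.
- Appendix 13 strongly encourages participants with drug-induced aseptic meningitis to stay in the study even if IMP is stopped.
- SAP Section 5.2 takes the reason for treatment discontinuation and the reason for study termination from different CRF pages. SAP Section 5.6.2.2 lists the two separately for adverse events.

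**Step 4: does follow-up differ in practice?** Only slightly. The Synopsis (Treatment Groups and Duration) covers "Study participants who complete the 24-week Treatment Period or prematurely discontinue IMP", and Section 4.1 says such participants "will undergo the EOT Visit/EDisc Visit and enter the SFU Period". Section 1.3 adds that anyone with an EDisc Visit should "complete the SFU phone call and EOS Visit at 3 and 7 weeks after the EDisc Visit". The SAP's text on study periods also sends participants withdrawn during the Treatment Period into the SFU. No lost contacts can be claimed.

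**Step 5: effect on the primary endpoint.** Table 9-1 counts permanent IMP discontinuation as failure under the composite strategy. Study withdrawal also ends IMP, so the result is failure on both routes and the difference is 0.

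**Step 6: effect on disposition.** Protocol Section 9.3.4 reports the proportion withdrawn from the study by treatment group. SAP Section 5.2 reports disposition by group and overall.

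- Planned: 68 randomized 1:1, so 68/2 = 34 per arm. One participant coded differently shifts an arm's proportion by 1/34 = 0.029, or 2.9 percentage points.
- Actual: 12 randomized (SAP Section 3). One participant shifts the overall proportion by 1/12 = 0.083, or 8.3 points. The arm split is not given, so the per-arm shift cannot be computed.

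**The case against.** The strongest reply is that footnote g is loosely worded and does not set a rival rule.

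- **Loose terminology.** Section 4.2 says participants with absent or lost clinical benefit must be withdrawn, where Section 7.1.3 means stopping IMP. Footnote q ties study withdrawal to the EDisc Visit, which every early discontinuer has. Section 4.4 speaks of discontinuing the study and then continues with the SFU call and the EOS Visit. The SAP's text on study periods does much the same.
- **Discretion.** Section 7.2 lets the investigator withdraw a participant at any time for safety.
- **Compatibility.** Withdrawing someone from the study also stops IMP, so a site that follows footnote g does not breach Section 7.1.2.
- **Size.** The percentage shifts assume an event that occurs and is coded differently. The planned arm size was not reached. SAP Section 5.6.3.10 only lists C-SSRS data, and with 12 participants any case can be read individually.

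The points on size stand and keep this minor. The points on terminology show that footnote g may well be a slip, but they do not reconcile it with Section 7: it names the study explicitly, and Section 7 separates the two actions. Discretion under Section 7.2 cannot explain a footnote that makes withdrawal mandatory. Compatibility runs one way only, because a site that follows Section 7.1.2 alone departs from footnote g.

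**Conclusion.** The inconsistency is real and is in current text. Footnote g makes study withdrawal mandatory for an on-study Yes to Question 4 or 5, Section 7.1.2 makes only IMP discontinuation mandatory, and Section 7.2.1 omits the event.

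Its weight is minor. Dosing, referral and the primary endpoint are the same on either route, and no loss of follow-up is claimed. What remains is weaker SFU wording on one route and a possible coding difference. The figures of 2.9 points (planned arm) and 8.3 points (12 randomized, overall) are conditional on one such event being coded differently; the documents give no event rate. The text mismatch is certain; the coding effect is only a possibility. With recruitment suspended at 12 participants, the benefit of a correction within this study is small.

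**What to change.** Reword footnote g so that a Yes to Question 4 or 5 leads to exclusion at Screening or, on study, to permanent discontinuation of IMP under Section 7.1.2, with immediate referral in both cases. Add one sentence: unless consent is withdrawn, the participant completes the EDisc Visit and enters the SFU Period, with the SFU call (AEs, concomitant medications and seizure diary, per footnote d) and the EOS Visit with C-SSRS.

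If study withdrawal is truly intended, leave the footnote and add the event to the mandatory list in Section 7.2.1 instead.

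The cost is the wording of one footnote and one added sentence. No new visits or procedures are needed.
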